## Secondary analysis:

1. Adverse Events will be analysed using Chi-squared test or a summary by presenting full listing and frequencies & percentages.

2. Quality of Life (QoL) questionnaires will be analysed using normality tests, descriptive statistics and reliability tests.

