## Secondary objective

The secondary objective of the study is to determine whether there is a timepoint during the

course of the day (phasing) that demonstrates the largest difference in IOP following heat and hypotensive eye drop combination.

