### 4.1.2 Secondary objectives:

1.Adverse events

2.QoL questionnaires

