## 5.2.2 Datasets

To determine whether there is a significant change in IOP in each participant, the IOP measured with and without the addition of heat over the five time points will be used in a one-way repeat measure ANOVA test will be completed for each day of phasing. A paired ttest will be used to establish significance between an individual's IOP measure at a certain time point with or without the addition of heat. A difference of 1.5mmHg in IOP mean deviation would be considered a significant change of IOP. This value has been used in previous Glaucoma studies (Allergan Bimatoprost SR and Thea In-Sight) to provide a 95% confidence interval. A paired t-test will be used to establish any significant change in BCVA at baseline and exit visit based on a mean SD change of 0.1 logMAR or 5 ETDRS letters. Ocular safety parameters, QoL (EQ-5D-5L) and OSDI questionnaires, visual fields and slit-lamp exam measures will be summarised for the cohort by mean, standard deviation (SD), median, minimum and maximum values. A non-parametric analysis (Wilcoxon signed rank test) will be used if the data is found to not be normally distributed. Ocular adverse events and safety variables will be tabulated by whether the participant has received heat treatment or not before instilling their anti-hypotensive eye drops. Normality of the data will be checked by plotting histograms of the data (separately before and after the heat) and not using stats tests. Differences will be considered statistically significant P values less than 0.05.

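### Quality of life is a listed secondary objective, but none of its named analyses is stated as a within-patient comparison of heat with no heat, and the protocol contradicts itself on normality tests

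*Protocol*

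**What the plan says.** Protocol section 4.1.2 gives two secondary objectives, the second being "2.QoL questionnaires", with no further wording. The heading Secondary objective earlier in section 4 (and the study summary) states a different one: to "determine whether there is a timepoint during the" day at which the IOP difference is largest.

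Section 5.2.1, Secondary analysis, item 2, says that the QoL questionnaires will be "analysed using normality tests, descriptive statistics and reliability tests".

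Section 5.2.2 names the instruments, "QoL (EQ-5D-5L) and OSDI questionnaires", and places them in a list with ocular safety parameters, visual fields and slit-lamp measures that "will be summarised for the cohort by mean, standard deviation (SD), median, minimum and maximum values". The same section says that normality will be checked with histograms "and not using stats tests".

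The Schedule of Procedures (Appendix 2) has separate rows for the QoL and OSDI questionnaires. Both are marked at Visit 1 (no heat), Visit 2 (heat) and Visit 3 (mask without heat).

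**The concern.** The design gives each completing patient a QoL score under three conditions, so a within-patient comparison is available at no extra cost. The methods named for QoL do not use it. A normality test describes the shape of a distribution. A reliability test describes how consistently a questionnaire measures. A cohort summary describes level and spread. None of these, as worded, estimates what changed when heat was added.

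This is more than a detail left for a statistical analysis plan. The protocol has a numbered item that names the QoL methods, and a later plan that followed it literally would inherit the mismatch. The report could then give reliability statistics from 24 people under a secondary-objective heading without showing a paired heat difference. Separately, an analyst cannot obey both sections on how normality is to be judged.

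**Working it through.** The protocol gives no effect size, SD or power for QoL, so there is no stated figure to reproduce. The check is mainly a comparison of texts.

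**1. What section 5.2 names for each measure**

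| Measure | Method named | Comparison stated? |
|---|---|---|
| IOP | Paired t-test at a time point (5.2.2) | Yes, with or without heat |
| Visual acuity | Paired t-test (5.2.2) | Yes, baseline against exit visit |
| Ocular adverse events and safety variables | Tabulation (5.2.2) | Yes, by heat or no heat |
| QoL | Normality tests, descriptive statistics, reliability tests (5.2.1); cohort summary (5.2.2) | None stated |
| OSDI | Cohort summary (5.2.2) | None stated |

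The protocol states a comparison for the first three rows. It mentions QoL and OSDI in the same section and states none for them.

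**2. Whether the Wilcoxon sentence fills the gap**

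In section 5.2.2 a sentence providing for the Wilcoxon signed rank test follows the questionnaire summary. It names no variable. The primary analysis in 5.2.1 pairs the same test with the paired t-test as its non-normal alternative, so the natural reading is a fallback for the t-tests already named. If it is taken to include QoL, it applies only when the data are not normal. No parametric counterpart is named for QoL, and the two visits to be compared are not given.

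**3. Normality**

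Section 5.2.1, item 2, prescribes normality tests for QoL. Section 5.2.2 prescribes histograms and excludes tests, with no exception for QoL. Both cannot be followed.

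**4. Precision of a paired difference (illustration only)**

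Inputs: n = 24 (section 7.2.1). The SD of the within-patient QoL difference is not given, so the result is in units of that SD. A two-sided 95% interval is assumed.

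Half-width = t(0.975, n − 1) / √n

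- n = 24: 2.069 / 4.899 = 0.42 SD
- n = 20 (assumed completers): 0.47 SD
- n = 18 (assumed completers): 0.50 SD

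These values hold for any paired mean with that many pairs. They show what the data could deliver and do not measure the size of a defect.

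**The case against.** Three stronger readings are tempting, and the text does not support them.

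- A reader might infer that QoL scores from the three visits will be pooled. Section 5.2.2 speaks of a summary for the cohort, which can simply mean the group as opposed to the individual. The schedule collects the forms visit by visit, so summaries by visit are a fair reading. They would give the mean difference by subtraction among the same patients, but not its paired interval.
- A reader might infer that the plan excludes any heat comparison for QoL. The unassigned Wilcoxon sentence could be stretched to cover it. The histograms are to be drawn separately before and after heat, which presumes data split by condition. The questionnaires also share a list with ocular safety parameters, and safety variables are tabulated by heat or no heat. Whether the questionnaires count among those is unclear.
- A reader might infer that the objective goes unanswered. Section 4.1.2 states no contrast or direction for QoL, so descriptive statistics do not contradict it. The other statement of the secondary objective in section 4 does not mention QoL at all.

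It is also fair to say that descriptive reporting suits a 24-patient feasibility study, that table layout is usually settled in an analysis plan, and that reliability statistics do no harm in themselves. OSDI is kept apart from QoL in 5.2.2 and in the schedule, so item 2 as written does not cover it.

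These arguments limit the weight of the point but do not remove it. Item 2 still names methods of which two describe the instrument or the distribution, and no comparison is stated. The contradiction on normality tests depends on none of these readings.

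**Conclusion.** The point stands as a minor mismatch between a listed objective and its named methods. Neither 5.2.1 nor 5.2.2 states a within-patient comparison of heat with no heat for QoL, although the data for one will be collected. The general Wilcoxon sentence does not reliably supply it. The clash between normality tests in 5.2.1 and histograms without tests in 5.2.2 is a plain contradiction.

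The consequence is small. The primary IOP conclusion, the sample size and the safety reporting do not depend on it. The 0.42 SD half-width assumes 24 complete pairs and an SD that the protocol does not give, so it is illustrative only. The conclusion assumes that QoL is meant to be a secondary objective, as section 4.1.2 and item 2 of the secondary analysis both treat it, despite the different objective stated elsewhere in section 4.

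**What to change.** Reword item 2 of the secondary analysis along these lines: EQ-5D-5L and, as a separate measure, OSDI will be summarised by visit. For each, the within-patient difference will be reported with its 95% confidence interval, for heated mask minus unheated mask and for heated mask minus no mask. These results are descriptive.

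Remove the normality tests from item 2 so that it agrees with section 5.2.2. Do not present reliability statistics as the analysis of the QoL objective; if they are wanted to inform a larger study, label them as such. Because item 2 now covers QoL only, the new wording should say openly that OSDI is being added.

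The visits run in a fixed order, so each difference also carries any effect of visit order. That is a further reason to keep the reporting descriptive.

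The cost is a short rewording of one item and a little more analysis. It needs no new data, visits or patients.

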## 5.2.2 Datasets

To determine whether there is a significant change in IOP in each participant, the IOP measured with and without the addition of heat over the five time points will be used in a one-way repeat measure ANOVA test will be completed for each day of phasing. A paired ttest will be used to establish significance between an individual's IOP measure at a certain time point with or without the addition of heat. A difference of 1.5mmHg in IOP mean deviation would be considered a significant change of IOP. This value has been used in previous Glaucoma studies (Allergan Bimatoprost SR and Thea In-Sight) to provide a 95% confidence interval. A paired t-test will be used to establish any significant change in BCVA at baseline and exit visit based on a mean SD change of 0.1 logMAR or 5 ETDRS letters. Ocular safety parameters, QoL (EQ-5D-5L) and OSDI questionnaires, visual fields and slit-lamp exam measures will be summarised for the cohort by mean, standard deviation (SD), median, minimum and maximum values. A non-parametric analysis (Wilcoxon signed rank test) will be used if the data is found to not be normally distributed. Ocular adverse events and safety variables will be tabulated by whether the participant has received heat treatment or not before instilling their anti-hypotensive eye drops. Normality of the data will be checked by plotting histograms of the data (separately before and after the heat) and not using stats tests. Differences will be considered statistically significant P values less than 0.05.

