The patient will attend the clinic for three separate visits each approximately one week apart. starting with phasing 'without heat', then phasing 'with heat' and lastly phasing wearing the Blephasteam mask but with no heat as a control. The Blephasteam mask will only be used on the days of the clinic visits, the participants will not be required to use the device at home. The water carrier inserts for the masks will be designated to the same patient throughout the study for hygiene reasons. The inserts for the mask will be moistened and fitted according to the manufacturers' instructions. The wireless device will be left to reach temperature for 3-4 minutes then the patient will be asked to wear the mask and be instructed to keep their eyes closed, this occurs once at the start of each visit. The device warms the ocular surface for a set time of 10 minutes, after which the participants will remove the mask and instil their habitual Glaucoma eyedrops. They will be instructed to close their eyes and apply light pressure on the inner corner of the eye for 30 seconds. The IOP will then be measured at the first time point with the ORA and Goldman devices. Although both eyes will be treated with the heat mask only the right eve results (to eliminate bias) will be used for the statistical analysis. During the visits the patients' will have their best corrected visual acuity (BCVA) reviewed before and after measurements are taken. IOPs are measured first using the ORA tonometer (Reichert Inc., Germany) followed by the Goldman tonometer (Haag-Streit AG, Switzerland) five minutes later as per previous studies measuring IOP with the sequential use of tonometers (Tejwani et al., 2015). These IOP measures are taken at five set time points during the day called 'phasing': 08:30 +/- 30 mins, 10:30 +/- 30 mins, 12:30 +/- 30 mins, 14:30 +/- 30 mins and 16:30 +/- 30 mins. An average of three measures will be taken using the ORA machine, when using the Goldman tonometer three measures will only be taken if the first two are not within >2mmHg of each other. The procedure for the Goldman tonometer will be as follows: Two individuals (an operator and a reader) will perform the readings for the study visits. The operator will be responsible for operating the slit lamp, tonometer, and the instrument dial, while the reader will read and record the results. A full anterior segment slitlamp examination will be performed at the end of each phasing visit to ensure there are no adverse effects experienced following the treatment, including grading of the Meibomian glands (Efron scale). Additional assessments include adverse events and quality of life and ocular questionnaires.

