### Primary analysis:

1. Mean difference of IOP will be analysed using paired t-test if normally distributed or using Wilcoxon signed rank test for pared cases if not normally distributed.

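### The per-day one-way ANOVA in section 5.2.2 tests time of day and cannot test heat; a condition-by-time model and a normality check on paired differences should replace what is written

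*Protocol*

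**What the plan says.** Section 5 of the protocol gives every participant three phasing visits in one fixed order, "starting with phasing 'without heat', then phasing 'with heat' and lastly phasing wearing the Blephasteam mask but with no heat as a control". The study flow chart shows the same order. Within each visit, "These IOP measures are taken at five set time points during the day called 'phasing".

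Section 5.2.2 states the purpose of the ANOVA: "To determine whether there is a significant change in IOP in each participant, the IOP measured with and without the addition of heat" is to be used over the five time points. The method it names is a "one-way repeat measure ANOVA test will be completed for each day of phasing". The same section adds paired t-tests of heat against no heat at a given time point.

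The primary analysis in section 5.2.1 is separate: "Mean difference of IOP will be analysed using paired t-test if normally distributed", with the Wilcoxon signed rank test otherwise. Section 5.2.2 is the only place that says how normality of the IOP data is judged: "Normality of the data will be checked by plotting histograms of the data (separately before and after the heat"), without formal tests.

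For safety, section 5.2.1 says "Adverse Events will be analysed using Chi-squared test or a summary by presenting full listing and frequencies & percentages". Section 5.2.2 tabulates ocular adverse events by whether heat was received.

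**The concern.** The ANOVA's stated purpose and its structure do not match. The purpose is a comparison with and without heat, but the analysis is split by day, and the day is what separates heat from no heat. A reader of the results could take a significant heat-day ANOVA as evidence for heat when it shows only that IOP varied between 08:30 and 16:30. A non-significant one says nothing against heat.

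The secondary objective in section 4 is also affected. It asks at which time point the heat difference is largest, which is a condition-by-time question. Per-day ANOVAs cannot answer it. Separate paired t-tests estimate the heat difference at each time but do not compare those differences across times.

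Two smaller mismatches have the same root, the paired structure of the data. The choice between paired t-test and Wilcoxon is tied to plots of the wrong quantity, and a chi-squared test is offered for adverse events that come from the same patients under both conditions.

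**Working it through.** **Inputs from the protocol.** 24 participants (section 7.2.1); three visits with one condition each, five times per visit (section 5); reference difference 1.5 mmHg and significance level 0.05 (section 5.2.2). The protocol gives no SD, correlation, diurnal profile or adverse-event rate and has no power calculation to reproduce.

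**Assumed for illustration.** SD 3 mmHg between patients, 1 between visits, 1.5 residual. The day is either flat or follows +1.5, +0.75, 0, −0.5, −0.75 mmHg across the five times.

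**1. What the per-day ANOVA tests.** For one day, with participant i and time j:

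F = [n Σⱼ(Ȳ.ⱼ − Ȳ..)² / 4] / [Σᵢⱼ(Yᵢⱼ − Ȳᵢ. − Ȳ.ⱼ + Ȳ..)² / 92], with n = 24 and 23 × 4 = 92 residual degrees of freedom.

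If heat lowers every reading that day by δ, then Yᵢⱼ, Ȳᵢ., Ȳ.ⱼ and Ȳ.. all fall by δ. Every bracket is unchanged, so F does not depend on δ. This needs no assumed SD.

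With the diurnal profile, the mean is 0.2 and the squared deviations sum to 1.69 + 0.3025 + 0.04 + 0.49 + 0.9025 = 3.425. The noncentrality is 24 × 3.425 / 1.5² = 36.5, and the power of the F test on 4 and 92 df is 99.9%, whatever heat does.

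Simulation (5,000 runs), proportion significant:

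| Heat effect | Day profile | ANOVA, heat day | Paired t-test, day means |
|---|---|---|---|
| 0 | flat | 4.9% | 5.2% |
| 1.5 mmHg | flat | 5.1% | 98.7% |
| 3 mmHg | flat | 5.5% | 100% |
| 0 | diurnal | 99.9% | 5.2% |

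The last column can be checked directly. The SD of the difference in day means is √[2(1² + 1.5²/5)] = √2.9 = 1.70, the standard error is 1.70/√24 = 0.348, and 1.5/0.348 = 4.3, which gives power of about 98.5% on 23 df.

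**2. Normality.** The paired t-test assumes normal differences D = Y(heat) − Y(no heat). With a skewed patient level common to both days, each condition had skewness of about 1.67 and the difference 0.00. In a constructed converse case both conditions were normal (excess kurtosis 0.01) and the difference was not (27). Separate histograms can mislead in either direction. The cost is small because the fallback is also a paired test. With normal differences of SD 1.70 and n = 24, power is about 98% for both tests at 1.5 mmHg and about 78% (t) against 76% (Wilcoxon) at 1.0 mmHg.

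**3. Adverse events.** With an assumed 30% rate under both conditions, the type I error of chi-squared at a nominal 5% was 4.8%, 1.8%, 0.3% and 0.2% at latent within-patient correlations of 0, 0.5, 0.8 and 0.9. In an example with 14/24 against 8/24 and six discordant pairs all one way, chi-squared gives P = 0.082. Exact McNemar gives 2 × 0.5⁶ = 0.031.

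**4. Can visit number enter a replacement model?** Everyone has no mask at visit 1, heat at visit 2 and the unheated mask at visit 3. The fixed-effects matrix for condition × time has rank 15 in 15 columns. Adding visit number keeps rank 15 with 16 columns (linear) or 17 (factor). Visit number is fully aliased with condition and cannot be estimated.

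**The case against.** The strongest reply is that heat is tested properly elsewhere. The primary analysis is a paired t-test or Wilcoxon signed rank test on the mean IOP difference, and section 5.2.2 adds paired t-tests at time points. Both suit within-patient data. This stands. A reader might infer that a real, constant heat effect would go undetected, and the documents do not support that. The paired comparison of day means that reaches about 98.7% in the table is close to the planned primary test.

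The ANOVA sentence is also garbled, and its opening words suggest that heat was meant to be a factor. That is plausible, but a one-way analysis run day by day still cannot contain heat, so the wording needs correcting.

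A reader might also infer that chi-squared would make adverse events falsely significant. With positive within-patient correlation it errs the other way. With independent conditions, exact type I error is 0.2%, 1.8%, 4.7% and 5.4% at event rates of 2%, 5%, 10% and 20%. Section 5.2.1 already offers a descriptive summary instead.

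It is tempting as well to say that pooling POAG and OHT patients must produce two-humped histograms. The protocol gives only upper IOP limits (24 and 30 mmHg) in patients controlled on treatment, so the separation of the two groups is unknown. The normality tests prescribed for the questionnaires do not clearly contradict the histogram rule, which is framed around before and after heat.

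**Conclusion.** The point holds in a limited form. The per-day one-way ANOVA cannot serve its stated purpose. This follows from the design alone; the percentages above depend on assumed SDs and an assumed diurnal profile. What is affected is this ANOVA and the secondary time-point question. The primary test of heat is not affected.

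The normality check is on the wrong quantity, but the choice of test makes a difference of about two percentage points of power or less in the normal case examined. The chi-squared option is a minor mis-specification, generally conservative, and disappears if the descriptive option is used.

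For a 24-patient feasibility study with an intact primary test, this should be corrected before analysis, but it does not invalidate the plan.

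**What to change.** - **ANOVA.** Replace the per-day ANOVAs with one within-patient model of right-eye IOP. Fixed effects: condition (no mask, heated mask, unheated mask), time point, and condition × time. Random effects: participant and participant-by-visit. The condition contrasts address heat, and the interaction addresses the secondary objective.
- **Visit order.** Leave visit number out. State that condition effects cannot be separated from visit order under the fixed sequence; only a change of design could separate them.
- **Normality.** Judge it on the paired differences or the model residuals, by plot if preferred.
- **Adverse events.** Use the listing with frequencies and percentages by condition that section 5.2.1 already allows. If a test is wanted, use exact McNemar for heat against one no-heat visit instead of chi-squared.

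The cost is a few sentences in sections 5.2.1 and 5.2.2. No extra data or visits are needed, and standard software fits the model.

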## 7.2.1 Size of sample

This is a feasibility study and as such a sample size of 24 participants has been selected for this quantitative research and this has been based on the figures previously cited by Sim and Lewis (2012) and Julious (2005) and also taking into account the budget available for equipment. The average of the IOPs measures taken at each time point with the ORA or Goldman tonometer and with and without the addition of heat will be used for statistical analysis.

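### The one analysis that names visual acuity tests a mean shift from baseline to exit, so it is insensitive to loss in a few patients and looks two to three weeks after the heat

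*Protocol*

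**What the plan says.** Section 5.2.2 (Datasets) gives BCVA this analysis: "A paired t-test will be used to establish any significant change in BCVA at baseline and exit visit based on a mean SD change". The threshold is a "mean SD change of 0.1 logMAR or 5 ETDRS letters", and the general significance rule is "Differences will be considered statistically significant P values less than 0.05". A Wilcoxon signed rank test replaces the t-test if the data are not normal.

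The same section promises cohort summaries (mean, SD, median, minimum, maximum) of ocular safety parameters, and a tabulation of ocular adverse events and safety variables by whether heat was given. BCVA is named in neither. Section 5.2.1 offers a full adverse event listing as one of two options.

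On collection, section 5 says patients will have their "best corrected visual acuity (BCVA) reviewed before and after measurements are taken" during the visits. The Schedule of Procedures marks BCVA once each at visit 1 (no heat), visit 2 (heat), visit 3 (mask without heat) and visit 4 (safety check), and not at identification and consent. The phasing visits are about one week apart, and the final visit comes one to two weeks after them. Section 7.2.1 gives the size: "a sample size of 24 participants has been selected for this quantitative research".

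**The concern.** The study title covers safety as well as efficacy. Heat could harm vision in a few patients, or only for a short time. A test of the cohort mean is weak against the first, and a contrast that ends weeks after the exposure is weak against the second. The stated threshold adds a third difficulty: a mean and an SD are different quantities, so the analyst cannot tell what is to be compared with 0.1 logMAR. A report that follows the sentence as written could state that acuity did not change significantly when several patients had lost lines of vision.

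**Working it through.** **Inputs.** From the protocol: n = 24, paired t-test, alpha 0.05, threshold 0.1 logMAR. Sidedness is not stated; I assume two-sided, so the critical value is t(23) = 2.069. The protocol gives no SD of BCVA change and no power for this test, so there is no figure of its own to reproduce. Where noise matters I assume an SD of change of 0.04 to 0.10 logMAR.

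**Loss in a few patients, no noise.** If k of n patients lose the same amount d and the rest do not change, the mean is kd/n and the sample variance is d²·k(n−k)/[n(n−1)]. The loss cancels: t = √[k(n−1)/(n−k)].

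| k of 24 | t | p |
|---|---|---|
| 1 | √(23/23) = 1.00 | 0.33 |
| 2 | √(46/22) = 1.45 | 0.16 |
| 3 | √(69/21) = 1.81 | 0.083 |
| 4 | √(92/20) = 2.14 | 0.043 |

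Example: three patients lose 0.2 logMAR (10 letters). The mean is 0.025, the SD 0.068, and t = 0.025/(0.068/√24) = 1.81. The Wilcoxon fallback gives 0.083 for three equal losses by the normal approximation, or 2 × (1/2)³ = 0.25 exactly with zeros dropped.

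**The 0.1 threshold read as a mean.** One patient losing 0.3 moves the mean by 0.3/24 = 0.0125. To reach 0.1, 0.1 × 24/0.3 = 8 patients must each lose 0.3.

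**With noise** (40,000 simulated trials at each assumed SD from 0.04 to 0.10), the chance of a significant worsening is:

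- no true loss: about 2.5%
- one patient losing 0.3: 2.0% to 4.5%
- three patients losing 0.3: 15% to 18%
- four patients losing 0.3: 27% to 46%

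If the mean must also reach 0.1, the chance is at most 0.1% with three such patients and 0.7% with four. A uniform shift of 0.1 in everyone is found with power above 99%. The weakness therefore concerns loss in individuals and not a general shift.

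**Timing.** Heat is applied at visit 2. Visit 3 is about one week later and exit is one to two weeks after that: 1 + (1 to 2) = 2 to 3 weeks.

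**What a count would give.**

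- Chance of seeing at least one case: 1 − 0.95²⁴ = 71% at a true risk of 5%; 1 − 0.90²⁴ = 92% at 10%.
- Exact 95% intervals: 0/24 has an upper limit of 1 − 0.025^(1/24) = 14.2%; 1/24 gives 0.1% to 21.1%; 3/24 gives 2.7% to 32.4%.

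**The case against.** **Other outputs may cover BCVA.** Section 5.2.2 tabulates safety variables by heat, and BCVA is naturally one of them. A reader might infer that heat-day BCVA is not analysed at all. The documents do not support that; they show only that BCVA is not named in the tabulation. Nor do they say whether the minima and maxima are of levels or of changes. An adverse event listing may also catch a loss.

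**A before-and-after-heat pair may not exist.** The text speaks of readings before and after measurements, which in context are tonometry, and the schedule has one mark per visit. This stands.

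**Left eyes.** The protocol says "only the right eve results (to eliminate bias) will be used for the statistical analysis" although both eyes are heated, so a reader might infer that left-eye losses drop out. That sentence sits in the IOP description, and section 4.1.1 ties the right eye to the IOP outcome. Nothing confines safety tables to right eyes.

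**No claim of safety from p > 0.05.** The protocol never says that a non-significant result shows safety. That stands; the caution below concerns how the result will be read.

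**Noise in a count.** With no true loss, independent eyes and an SD of change of 0.04 to 0.10, a change of 0.1 or more occurs in about 0.6% to 16% of eyes. In either eye of a patient that is 1% to 29%, or 0.3 to 7 of 24. A bare count could suggest harm that is not there. This also stands, and is why the count needs a comparator.

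**The statistical analysis plan.** Detailed safety tables commonly belong there, and it is not shown. The point rests on a rule that the protocol does state, not on a missing table.

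**Conclusion.** The point holds in this limited form: the only analysis naming BCVA uses an undefined threshold, is insensitive to loss in up to three of 24 patients (p ≥ 0.083 when the losses are equal and the rest unchanged), and uses a contrast about two to three weeks after the single heat exposure, while BCVA is scheduled closer to it. The no-noise result rests on a two-sided test; the 15% to 18% detection rate for three patients losing 0.3 rests on the assumed SD range. Other safety outputs may partly cover the gap. It is a cheap improvement worth making, and does not invalidate the design.

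**What to change.** Replace the BCVA sentence in section 5.2.2 so that it does the following:

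- Define baseline as visit 1, since no BCVA is scheduled at consent.
- Replace the threshold phrase with mean change and its 95% CI.
- Name BCVA among the safety variables tabulated by visit and heat condition.
- Report each patient's change from visit 1 to the heat visit, the unheated-mask visit and exit, for each eye measured. Add the same-day before/after change where both readings exist, and state when those readings are taken.
- Give the number of patients losing at least the protocol's own 0.1 logMAR (5 letters) with an exact 95% CI, beside the same count at the unheated-mask visit, so that measurement noise can be judged.
- State that a non-significant mean test is not evidence of no vision loss.

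The cost is one paragraph of wording; the changes from visit 1 use readings already scheduled. The price is wide intervals (even 0/24 leaves an upper limit of 14.2%) and some counts due to test-retest noise. The unheated-mask visit always follows the heat visit, so any effect lasting a week would appear in both counts; the comparison is a gauge of noise, not a randomised control.
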